## TASMANIAN SCIENTIFIC RESEARCH ADVISORY COMMITTEE

Ascorbic Acid (Vitamin C) & Sodium ascorbate (125.3mg) equiv. Ascorbic Acid (Vitamin C)110mg)	390 mg + 110= 500mg
Rutin	100 mg

Participants will be asked to complete a logbook to record the day and time they take the capsules. Participants will be asked not to change any other lifestyle factors (e.g. diet or level of physical activity). During the last week of the Thompson's Super Bioflavonoid Complex® supplementation/Placebo study, they will be asked to repeat the food questionnaire and the physical activity questionnaire. This will be filled out at home and brought to the clinic on visit 2.

*Pharmacokinetics/pharmacodynamic study:*

During visit 1, and after the first dose of Thompson's Super Bioflavonoid Complex® supplementation/ Placebo, additional blood and urine samples will be collected following the first dose of the supplement to measure the pharmacokinetics/pharmacodynamics characteristics of a single dose administration of the citrus bioflavonoid in human body. A series of blood and urine samples will be collected at times (0, 1, 2, 4, 8 and 24) hours. Participants will be able to move around and stay within the clinical area for the first 4 hours, and they can leave and come back for the 8 hrs and 24 hrs time of collection.

Commented [HA1]: All, please amend this as you think more appropriate.

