Bioflavonoids are classified as organic polyphenolic compounds, which are found in various plant-based foods in different concentrations, like berries and citrus fruits. Citrus bioflavonoids can be specified as plant pigments available in various sources such as oranges, lemons and grapefruits. They have the capability of enhancing the absorption levels as well as the utilisation of vitamin C [8]. Thompson's Super Bioflavonoid Complex® contains citrus bioflavonoid extract-500 mg, ascorbic acid-390 mg, rutin-100 mg, and sodium ascorbate-125.3 mg (equiv 110 mg Ascorbic Acid). Lemon bioflavonoid is the source of eriocitrin [9], which possesses a lipid lowering activity as seen in animal models [9]. Orange bioflavonoid comprises hesperetin, hesperidin and naringenin [10]. These possess potent antioxidant activity as seen in previous studies [11]. Other *in-vivo* studies signified the impact of naringenin and hesperidin in suppressing macrophage infiltration [11], and reducing blood glucose levels [12]. The grapefruit bioflavonoid contains mainly naringenin, which is beneficial in reducing arterial stiffness in post-menopausal women [13], and helps improving hyperglycaemia [14]. A more recent study investigated the effects of diabetinol (nobiletin-49%, tangeretin-13%, including limonoids, tocotrienols and vitamin E) on glycaemic control in patients with impaired fasting glucose [15].

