**VISIT 1:****Finger Prick Method**

A finger prick will be performed on the participants to test their blood glucose level using glucometer

Participants will undergo a variety of metabolic and blood pressure measurements. Participants will fast ( $\geq 12$  hours) and refrain from caffeine and alcohol ( $\geq 12$  hours) and refrain from exercise for 48hrs prior to attending the clinic at 8:00-10:00am. T2D participants on metformin will be instructed to discontinue their medication for treating hyperglycaemia on the morning of the study. Testing will be conducted on participants in a quiet, temperate room and in the supine position. A polyethylene catheter will be placed in an antecubital vein for blood sampling. Menstruating females will only be tested in the early follicular phase.

*Clinical Biochemistries*

A blood sample (0.33M EDTA tubes) will be taken to measure clinical chemistries (glucose, insulin, lipids and HbA1c). A second blood sample will be taken, centrifuged at 4°C for 10 minutes, and plasma/serum samples stored at -80°C for analysis of other metabolite, inflammatory markers

*Urine sample*

We will also measure urinary electrolytes (e.g. sodium, potassium, creatinine, albumin), markers of oxidative stress (e.g. 8-Hydroxy-2'-deoxyguanosine) and kidney function. A spot urine sample will be taken at rest and 2hrs following the OGTT.

In addition, spot urine samples will be taken every 4 weeks during the study.

Oral glucose tolerance test (OGTT)

A 2-hour OGTT will be performed to assess glucose tolerance and insulin sensitivity and is a routine clinical test for determining insulin resistance and diabetes. A fasting blood sample (time: -10 minutes) will be taken prior to ingestion of a drink containing 25g of glucose (time: 0 minutes). Blood samples will also be taken at specific time points post-glucose ingestion (0, 30, 60, 90 and 120 minutes), thereby enabling measurement of 2-hour area under the curve (AUC) for glucose and insulin and insulin sensitivity indices.

Whole-body insulin sensitivity will be calculated according to the Matsuda index (17):

Insulin sensitivity =  $10,000 / \sqrt{[(FPG \times FPI) \times (\text{mean OGTT glucose} \times \text{mean OGTT insulin})]}$

Here, FPG represents fasting plasma glucose, FPI- fasting plasma insulin, and mean values the average of 0, 30, 60, 90 and 120-minute plasma concentrations.

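### The single-dose citrus-bioflavonoid series neither restricts nor records dietary citrus between 4 and 24 h, so the late samples, chiefly the 24 h one, can reflect diet as well as the capsule (minor)

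*Protocol*

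**What the plan says.** The pharmacokinetics/pharmacodynamic paragraph of the Protocol (Visit 1) gives the aim of the series as the "pharmacokinetics/pharmacodynamics characteristics of a single dose administration of the citrus bioflavonoid in human body". On timing it says: "A series of blood and urine samples will be collected at times (0, 1, 2, 4, 8 and 24) hours". Participants are to "stay within the clinical area for the first 4 hours", and then "they can leave and come back for the 8 hrs and 24 hrs time of collection". The paragraph applies to both the supplement and the placebo.

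On diet, the supplementation part of Visit 1 says: "Participants will be asked not to change any other lifestyle factors (e.g. diet or level of physical activity". The Visit 1 preparation rules (fast, caffeine, alcohol, exercise) apply "prior to attending the clinic at 8:00-10:00am", that is, before arrival only.

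On where the analyte comes from, the Background describes bioflavonoids as compounds "which are found in various plant-based foods in different concentrations, like berries and citrus fruits", and adds: "Citrus bioflavonoids can be specified as plant pigments available in various sources such as oranges, lemons and grapefruits". It names hesperidin, hesperetin and naringenin as constituents of orange, eriocitrin of lemon and naringenin of grapefruit.

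**The concern.** A single-dose series describes the dose only if the later samples contain little of the same substance from elsewhere. Here the substance is an ordinary food component, participants are away from the clinic for most of the 24 h, and their instruction is to eat as usual. A glass of juice or a piece of fruit in the evening or at breakfast adds the same compounds to the next sample. Nothing is recorded that would show afterwards whether this happened.

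At stake are the individual late concentrations and whatever is derived from them, such as AUC or a half-life. The 12-week comparison of glycaemia, DPP-4 activity and oxidative stress does not use these samples.

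**Working it through.** **1. Is dietary citrus controlled or recorded anywhere in the window?**

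| Provision in the Protocol | Covers food from 4 to 24 h? |
|---|---|
| Visit 1 preparation | No: applies before arrival and does not mention citrus |
| Exclusion criterion 12 | No: concerns supplements, not food |
| 3-day food record (eligibility visit) | No: completed at home before Visit 1 |
| Repeated food questionnaire | No: last week of supplementation |
| Usual-diet instruction | Works the other way: tells participants to carry on |

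Food in the first 4 h is not specified either, but participants are then in the clinical area. The time away from the clinic is up to 24 − 4 = 20 of 24 h (83%), apart from the 8 h return.

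**2. How much rests on the late samples?** Each linear-trapezoid weight is half the distance between the two neighbouring times (half the single adjoining interval at the ends):

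- 0 h: (1 − 0)/2 = 0.5
- 1 h: (2 − 0)/2 = 1
- 2 h: (4 − 1)/2 = 1.5
- 4 h: (8 − 2)/2 = 3
- 8 h: (24 − 4)/2 = 10
- 24 h: (24 − 8)/2 = 8

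The sum is 24. The 8 and 24 h samples carry (10 + 8)/24 = 75% of the weight. This is leverage, not a share of the area: it says how strongly an error in those concentrations feeds into AUC0-24.

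**3. How large could the effect be?** The Protocol gives no half-life, concentration or intake, so what follows is illustration. Assumptions: immediate absorption; one-compartment decay with half-life h = 3 or 6 h; one citrus serving equal to f = 5% or 15% of the study dose, taken at time s; the dose scaled to 1.

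- Capsule at time t: 2^(−t/h)
- Serving at time t > s: f × 2^(−(t − s)/h)
- Diet-to-capsule ratio after the serving: f × 2^(s/h)
- Half-life from the last two samples: 16 × ln 2 / ln(C8/C24)

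Example with h = 3, f = 0.05, s = 20. C8 = 2^(−8/3) = 0.1575. C24 = 2^(−8) + 0.05 × 2^(−4/3) = 0.0039 + 0.0198 = 0.0237. The ratio C8/C24 is 6.63, and 16 × 0.693/ln 6.63 = 5.9 h.

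| Serving taken at | Diet/capsule in the next sample, h = 3 | Same, h = 6 | Half-life found when 3 h is true | Half-life found when 6 h is true |
|---|---|---|---|---|
| 6 h | 0.20–0.60 (8 h sample) | 0.10–0.30 (8 h sample) | 3.0 | 6.0 |
| 10 h | 0.50–1.5 (24 h sample) | 0.16–0.48 (24 h sample) | 3.4–4.0 | 6.5–7.6 |
| 20 h | 5.1–15 (24 h sample) | 0.50–1.5 (24 h sample) | 5.9–12.2 | 7.7–12.0 |

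A serving before 8 h raises C8 and C24 by the same factor, so the half-life is unchanged.

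**4. Effect on AUC0-24 in the same model.** With the weights of step 2, the capsule alone gives 5.04 (h = 3) or 8.94 (h = 6).

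- Serving at 20 h adds 8 × f × 2^(−4/h). For h = 3 this is 0.159–0.476, or 3–9%. For h = 6 it is 0.252–0.756, also about 3–8%.
- Serving at 6 h adds f × [10 × 2^(−2/h) + 8 × 2^(−18/h)]. For h = 3 this is 0.321–0.964, or 6–19%. For h = 6 it is 0.447–1.341, or 5–15%.

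Early intake therefore affects AUC more and the half-life not at all. Late intake affects the half-life most.

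**The case against.** The strongest reply has five parts.

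- **The damage depends on timing and on assumed inputs.** This stands. The largest figures need the shorter half-life, the larger serving and intake 4 h before the last sample. A serving before 8 h causes no half-life bias, and at 8 h the capsule dominates in every case tried for a serving at 5–6 h (diet 0.09 to 0.60 of the capsule signal).
- **The PK paragraph names no parameter.** This stands. It mentions no analyte, elimination slope or urinary recovery, and no timed urine volumes are described. A reader might infer that slope, AUC tail and urinary recovery are all inflated. The Protocol does not support that: two of these are not stated endpoints, and late intake flattens a slope rather than inflating it.
- **Placebo participants appear to be sampled on the same schedule.** This stands for group means: randomisation makes the active-minus-placebo mean curve interpretable. It does not correct one person's curve for that person's unrecorded intake, and the Protocol does not state such a correction.
- **The 0 h sample and the fast of at least 12 h protect the baseline.** They do, but they say nothing about food eaten after the participant leaves.
- **The study figures and consent pages are not available here and might carry a food instruction.** That is possible. The finding concerns the protocol text, where such a rule would need to be reconciled with the usual-diet instruction. A statistical analysis plan could not restrict or record food afterwards.

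**Conclusion.** The point holds as a minor one. Followed as written, the plan lets dietary citrus enter the late samples, chiefly the 24 h one, without a restriction or a record. Individual pharmacokinetic estimates can be biased, because 75% of the AUC0-24 weight lies on the 8 and 24 h samples.

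The size cannot be determined from the Protocol. Under the illustrative assumptions it runs from no effect on half-life (intake before 8 h) to a half-life about four times too long (12.2 against 3 h), with AUC0-24 raised by up to about 19% in the cases shown for 6 and 20 h. These ranges rest on an assumed half-life, serving size and timing.

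A reader might conclude that the late samples measure diet rather than the capsule. The documents do not support that. The samples mix the two, in proportions that are unknown, and in many of the cases tried the capsule is the larger part. Nor does the point reach the randomised 12-week comparison: the series appears in neither the aim nor the hypothesis.

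**What to change.** In the pharmacokinetics/pharmacodynamic paragraph of Visit 1:

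1. State that, as an exception to the usual-diet instruction, participants avoid citrus fruit, citrus juice and citrus products from the 0 h sample until the 24 h sample.
2. Have them record all food and drink over that window on the food-record form already in use. The Background also names berries as a source of bioflavonoids, so the record should not be limited to citrus.
3. State that the late samples are analysed as active minus placebo, with a sensitivity analysis that leaves out late values from participants who report citrus.

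The restriction should start after the 0 h sample and not before the visit. A ban in the days before Visit 1 would put the baseline glucose tolerance and oxidative-stress samples on a different diet from those at Visit 2, which has no matching rule, while the Data analysis section plans paired before/after tests.

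The cost is a one-day diet restriction, one more use of an existing form, and possibly a few late samples set aside in the sensitivity analysis. No extra visit or assay is needed.

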**VISIT 2 - WEEK 12 TESTING:**

Following the 12 weeks of Thompson's Super Bioflavonoid Complex® supplementation/Placebo, participants will be asked to fast overnight (i.e. not eat food and only drink water on the morning of the study) and stop taking metformin and then at Medical Science Precinct/School of Health Sciences, UTAS. They will undergo an oral glucose tolerance test to measure your glucose tolerance and insulin sensitivity. This will require the participants to drink 25g of glucose (sugar drink) and then the sample of blood will be taken from their vein before and at 0, 30, 60, 90 and 120 min after drinking the glucose solution. Blood pressure and vascular health will also be measured using a blood pressure cuff placed on your upper arm of the participants as well as urine sample will be collected to measure kidney function, electrolytes and oxidative stress. The body composition measurement (height, weight, waist and hip circumference) will also take place.

***Quality control and feasibility***

It is worth to mention that this study was reviewed and updated several times during the successive meetings held between the PhD candidate and his supervisor. Besides, it has been discussed during the regular diabetes lab meeting and amended based on the feedback received from the researchers.

[name] undertook a phlebotomy course to upgrade his knowledge about the procedure and learned more about the risk management in this study. In addition, there will be experienced staff available in the clinical areas who will be willing to help and support in any form necessary for the study.

### Data analysis

Data analysis will be done using SPSS program (IBM SPSS Statistics version 22), and Microsoft Excel 2010. All values will be expressed as mean  $\pm$  SEM. Statistical analyses will be performed using a one-way ANOVA followed by unpaired Student's t test and paired students t-test (individual results before and after the course of supplements)-LSD- (Least significant difference) (non-parametric, with two-tailed) will be used for non-parametric results (to compare patients versus control results). Results will be considered significant at P equal or < than 0.05.

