## METHODS

### Design

**Participants:** Fifty participants recently diagnosed with prediabetes and/or T2DM living in Hobart/Launceston regions will be recruited for this study. The study will be conducted in two clinical areas: 1- Medical Science Precinct, University of Tasmania (UTAS), Hobart. 2- School of Health Sciences, Newnham campus, Launceston. Potential participants will be identified by local media, flyers, local General Practices, as well as by the Diabetes clinic at the Royal Hobart Hospital and Launceston General Hospital. Participants will undergo the following:

1. Medical & lifestyle questionnaires (general health, diet & physical activity questionnaires).
2. Anthropometrics (body weight, height, waist & hip circumference).
3. Blood tests to measure blood glucose, HbA1c, serum lipids, insulin, & oxidative markers (8-hydroxy deoxy Guanosine (8-OHdG), and resistin).
4. DPP-4 activity in the blood before and after 12 weeks.
5. Glucose metabolism (2hr oral glucose tolerance test).
6. Haemodynamic measures (blood pressure, heart rate & ECG).
7. Urinary electrolytes & kidney function.

**Research design:** This is a randomized double-blinded placebo-controlled study. The total duration of the recruitment process is 12 weeks.

Participants will be randomly allocated into two study groups (25 participants in each study group): Study group (Group-1) include participants who use the nutraceutical supplement (Thompson's Super Bioflavonoid Complex®) for 12 weeks and continue on their current anti-diabetic treatment with no interruption. Control group (Group-2) include participants who use the placebo capsules for 12 weeks and continue on their current anti-diabetic treatment with no interruption.

The placebo capsules would contain the same excipients as the active capsules, but the active herbal extract would be replaced by excipients.

The excipients in the Thompson's Super Bioflavonoid Complex are microcrystalline cellulose (BP), calcium hydrogen phosphate dehydrate (USP), silica – colloidal anhydrous (BP), crospovidone (BP) and magnesium stearate (BP).

As per the instruction provided, the supplements will need to be stored below 30 °C in a dry place.

[figure not shown]

Figure 1: Overview of the study.

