Our previous data shows that we had statistical significant changes in the levels of 8-OHdG and antioxidants using 40 T2DM patients [16]. Based on these data and assuming 20-25% withdrawal rate from the study, for a two sample test (t-test) with a Type I error of 5% ( $\alpha = 0.05$ ) and 80% power, we will require 50 participants in each group.

*Recruitment*

Potential participants will be identified by radio, flyers, local General Practices, and by the Diabetes clinic at the Royal Hobart Hospital/Launceston General Hospital. Potential participants may be contacted using the National Diabetes Services Scheme (NDSS) through Diabetes Tasmania. Participants from previous studies may be contacted if they have given consent to be contacted for future studies.

Participants who meet the inclusion/exclusion criteria will receive the participant information sheet/consent form inviting them to take part. Contact details of the study coordinator will be given, so that participants can raise any queries or concerns that they have and inform of their interest in participating in the study.

Participants from previous studies will be contacted via telephone, email or mail regarding the study and will be given the opportunity to contact the study coordinator if they are interested. Participants responding to online, print media and radio advertisements will be invited to contact the study coordinator by telephone or email. Initial screening will be based on a health history questionnaire and questions prior to attendance to rule out exclusion criteria.

[figure not shown]

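### The test named for non-parametric results, LSD, is parametric and in this two-arm trial is the unpaired t-test, so skewed outcomes would lose power

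*Protocol*

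**What the plan says.** The Data analysis section of the protocol sets out two routes. The general route is "Statistical analyses will be performed using a one-way ANOVA followed by unpaired Student's t test and paired students t-test". The route for outcomes that do not suit those tests is LSD: "Least significant difference) (non-parametric, with two-tailed) will be used for non-parametric results (to compare patients versus control results". LSD carries the label "non-parametric, with two-tailed", and the threshold is given as "Results will be considered significant at P equal or < than 0.05". The same section has all values presented as mean with SEM. The protocol names no rank-based test and no transformation.

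The Design section gives the comparison to which this applies: "Participants will be randomly allocated into two study groups (25 participants in each study group". The sample size justification is also built on a parametric test ("for a two sample test (t-test) with a Type I error of 5" per cent), "assuming 20-25% withdrawal rate from the study".

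**The concern.** The protocol expects some outcomes to be unsuitable for t-tests and sets a separate rule for them. The procedure named in that rule belongs to the family being avoided. LSD is a t-type comparison of means after ANOVA, and nothing in it protects against skewness or a few large values.

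Two things are at stake. First, power: a comparison of raw means is inefficient when data are strongly right-skewed, and the trial is small. Second, the rule cannot be followed consistently. An analyst who runs the named procedure gets a t-test, while one who follows the label runs a rank test. The two can disagree, so the choice could end up being made after the data are seen.

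This is a wrong statement in the protocol, not a detail left for a later analysis plan.

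**Working it through.** **Step 1. What LSD is with two arms.** With k groups of n, LSD declares two means different when their absolute difference exceeds t(0.975; kn − k) × √(MSE × 2/n), where MSE is the ANOVA within-group mean square. With k = 2, MSE is the pooled variance s² and the degrees of freedom are 2n − 2. The criterion becomes |difference| / (s√(2/n)) > t(0.975; 2n − 2), which is the unpaired Student's t-test. The one-way ANOVA gives F = t². All three are one test.

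- At n = 20 per arm the threshold is 2.024 × s × √(2/20) = 0.640 s, for LSD and t-test alike.
- On one simulated skewed data set (log-normal, 25 per arm), p = 0.189 for LSD, for the t-test and for ANOVA. Mann-Whitney gave p = 0.628. The direction of that gap means nothing in a single data set; it shows only that LSD is not a rank test.

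**Step 2. Inputs for the size of the effect.**

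- Two arms of 25 (Design), less 20% withdrawal, the lower end of the range in the sample size justification: 25 × (1 − 0.20) = 20 evaluable per arm.
- Two-sided alpha 0.05 (Data analysis) and 80% power (sample size justification).
- Distribution: none is given in the protocol. Assumed log-normal, with log-SD from 0.3 (mild skew) to 1.0 (marked skew).
- Effect size: none is given. Set so that a t-test on the log scale has 80% power. The normal approximation is (1.960 + 0.842) × √(2/20) = 0.886 log-SDs; the exact t-based value is 0.909, which was used.

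**Step 3. Type I error.** With identical skewed distributions in both arms, LSD (the raw-scale t-test) rejects in 0.049, 0.048, 0.044 and 0.038 of trials at log-SD 0.3, 0.5, 0.8 and 1.0. It is at or below the nominal 5% throughout.

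**Step 4. Power at 20 per arm.**

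| Assumed log-SD | LSD = raw t-test | Mann-Whitney | t-test on logs | Loss, LSD v Mann-Whitney |
|---|---|---|---|---|
| 0.3 | 78% | about 78% | 80% | about 0 points |
| 0.5 | 75% | 78% | 80% | 3 points |
| 0.8 | 68% | 78% | 80% | 10 points |
| 1.0 | 61% | 78% | 80% | 17 points |

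**Step 5. Sensitivity to sample size.** The sample size justification gives a different number: "we will require 50 participants in each group". That conflict with the Design section is a separate matter, but the pattern here does not depend on it. With a fixed shift of 0.8 log-SDs and log-SD 1.0, power for LSD against Mann-Whitney is 60% v 76% with 25 analysed per arm and 88% v 97% with 50.

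These simulations compare single-time values without baseline adjustment, so they show the direction and rough size of the loss. They do not predict the power for any named biomarker.

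**The case against.** **The sentence may be garbled.** It runs several methods together. LSD could be meant as the ANOVA post hoc procedure, with some unnamed two-tailed non-parametric test intended for the rest. That reading is possible, so one cannot be certain that every non-normal outcome would be given a t-test. It does not rescue the text: either the named test is wrong for its purpose, or the intended test is not named.

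**The consequence rests on assumed skewness.** This stands. The protocol reports no distribution for insulin, the insulin sensitivity indices, 8-OHdG, interleukin-6 or resistin. With mild skew there is practically no loss. The protocol does anticipate some non-parametric results, and those are exactly the ones this rule governs.

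**A reader might infer that LSD leaves the trial without error control.** The protocol does not support that. LSD is assigned to one contrast between two arms, where it holds the 5% level (Step 3). Its multiplicity weakness needs several groups or arm-by-visit cells compared pairwise. The protocol describes no such comparison: before-and-after results go to the paired t-test, and an ANOVA comes first.

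**Patients versus control.** Both arms consist of patients, so the phrase is loose. The Design section calls Group-2 the control group, however, so the intended contrast is clear and nothing rests on the wording.

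**Conclusion.** The point holds as a mislabelled method. The procedure prescribed for non-parametric results is parametric, and with the two arms of this trial it is the unpaired t-test under another name. As written, the rule gives skewed outcomes no alternative analysis.

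The cost is power, not false positives. Under the stated assumptions (log-normal data, 20 evaluable per arm, an effect with 80% power on the log scale) it runs from about 0 points against Mann-Whitney at log-SD 0.3 to about 17 at log-SD 1.0. That the text is wrong is certain; how much it matters for any one outcome is not, because skewness is assumed. The point should be corrected before analysis, but it does not threaten the validity of a positive two-arm result.

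**What to change.** Delete the LSD wording from the Data analysis section and put a valid method for skewed outcomes in its place:

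- a between-arm analysis of log-transformed week-12 values adjusted for the log baseline value, reported as a ratio of geometric means with 95% CI; or
- where no transformation works, a two-sided Mann-Whitney test comparing change between arms.

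State which method applies to each outcome, and settle this before unblinding. The protocol has no baseline-adjusted model at present, so the sentence should describe the model in full.

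The cost is a sentence or two. Both methods are available in SPSS, the package already named, and nothing changes for visits, samples or participants.

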**AIMS**

Aim 1-: To determine the effect of nutraceutical supplement (Thompson's Super Bioflavonoid Complex®) as natural DPP-4 inhibitor on glycaemic control in prediabetes and type 2 diabetes mellitus (T2DM).

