**HYPOTHESES**

Hypothesis 1-: Thompson's Super Bioflavonoid Complex® (*two capsules per day for 12 weeks*) will significantly reduce DPP-4 activity in prediabetes and type 2 diabetes, increasing incretin hormone levels, and improving the blood glucose response to a glucose challenge and reduce the degree of oxidative stress.

This study will investigate the potential of commercially available nutraceutical supplements (Thompson's Super Bioflavonoid Complex®, 500 mg (Citrus Bioflavonoid capsules, two capsules/day) to reduce blood glucose levels in patients with prediabetes and T2DM. The action of these supplements is thought to be similar to the dipeptidyl peptidase-4 (DPP-4) inhibitor group, also known as gliptins, which are second line anti-diabetic drugs after metformin and sulfonylureas. The gliptins block the action of DPP-4, an enzyme which inhibits a group of gastrointestinal hormones called incretins [1]. Incretins help stimulate the production of insulin when it is needed (e.g. post meal) and reduce the production of glucagon by the liver when it is not needed (e.g. during digestion). By protecting incretins, DPP-4 inhibitors help regulate blood glucose levels. Studies have shown that gliptins possess side effects which include (but not limited to) flu-like illness, joints pain, and pancreatitis [1]. Naturally derived DPP-4 inhibitors may offer an alternative to prescription based gliptins, or as "add on" therapy to first line products and decrease the risk of developing diabetic complications. This will also reduce the financial burden (total annual cost of the antidiabetic medicine is around AU\$193.8 million) [2].

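### No primary endpoint is designated, the power claim rests on markers that do not measure the aim, and one P ≤ 0.05 threshold covers every result

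*Protocol*

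**What the plan says.** Four places in the Protocol bear on what the trial is meant to show.

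- **Aims.** The one aim concerns the supplement's effect "on glycaemic control in prediabetes and type 2 diabetes mellitus (T2DM"). No variable or time point is attached to it.
- **Hypotheses.** The supplement "will significantly reduce DPP-4 activity in prediabetes and type 2 diabetes, increasing incretin hormone levels", and the sentence goes on to "improving the blood glucose response to a glucose challenge and reduce the degree of oxidative stress". The four components are not ranked, and the text does not say whether all of them or any of them must succeed.
- **Sample size Justification.** The basis is that "we had statistical significant changes in the levels of 8-OHdG and antioxidants using 40 T2DM patients". A two-sample t-test with 5% type I error, 80% power and 20-25% withdrawal is then said to need 50 per group. No effect size or standard deviation is given.
- **Data analysis.** After naming one-way ANOVA, unpaired and paired t-tests and LSD, it closes with "Results will be considered significant at P equal or < than 0.05". It does not separate primary from other outcomes.

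**The concern.** A confirmatory trial needs one stated answer to the question of which result decides it. Here the aim, the hypothesis and the sample size each put a different quantity first, and the significance rule treats every result alike. Two things follow.

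First, if HbA1c and the glucose tolerance test showed nothing but a lipid or urinary marker crossed 0.05, the protocol's wording would let that marker be reported as a significant result. It would give no rule for saying that the aim had failed.

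Second, the 80% power refers to oxidative markers. The reader learns nothing about the chance of detecting an effect on glycaemia.

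This goes beyond detail that a separate analysis plan could supply. The protocol itself fixes an undifferentiated threshold and itself ties its power to something other than its aim. An analysis plan that named a glycaemic primary endpoint would leave the sample size paragraph unchanged.

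**Working it through.** **1. The plan's own figure.** The stated 50 per group cannot be reproduced, because neither effect size nor standard deviation is given. It can only be solved backwards. With 20% withdrawal, 50 × 0.80 = 40 are evaluable per group; with 25%, 50 × 0.75 = 37.5. The standardised effect detectable with 80% power at two-sided 0.05 is d = (1.960 + 0.842) × √(2/n):

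- n = 40: d = 2.802 × √0.0500 = 0.63
- n = 37.5: d = 2.802 × √0.0533 = 0.65

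So 50 per group implies d of about 0.63 to 0.65 on whatever marker was meant, and the only markers named are 8-OHdG and antioxidants. Nothing links that d to HbA1c or glucose. The Design section plans 25 per group, which is a separate conflict. With 19 to 20 evaluable per group, power at d = 0.634 would be about 48% to 50% (noncentral t).

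**2. Count of outcomes under the one threshold**, from the Hypotheses, Design, Participants and Visit 1 sections:

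| Group | Outcomes | Number |
|---|---|---|
| Blood | glucose, HbA1c, lipids (counted once), insulin, 8-OHdG, resistin | 6 |
| Enzyme and hormones | DPP-4 activity; incretins (named in the hypothesis) | 2 |
| Further biomarkers | lipid peroxidation, interleukin-6 | 2 |
| OGTT | glucose AUC, insulin AUC, Matsuda index | 3 |
| Further insulin indices | muscle, hepatic, HOMA-IR | 3 |
| Haemodynamic | blood pressure (counted once), heart rate, ECG | 3 |
| Anthropometric | weight, waist, hip | 3 |
| Urine | sodium, potassium, creatinine, albumin | 4 |

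The total is 26. Twenty is used below as a cautious round number, and 5 as a short list close in length to the four-part hypothesis.

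**3. Chance of at least one false positive**, if any single result at P ≤ 0.05 were taken as success, with no true effect and one between-arm test per outcome.

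- Independent outcomes: 1 − 0.95^k. For k = 20, 1 − 0.358 = 0.642. For k = 5, 1 − 0.774 = 0.226.
- Equal correlation ρ between test statistics: 1 − ∫ φ(x) [Φ((1.96 − √ρ·x)/√(1−ρ)) − Φ((−1.96 − √ρ·x)/√(1−ρ))]^k dx, evaluated numerically.

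| Outcomes k | ρ = 0 | ρ = 0.3 | ρ = 0.5 | ρ = 0.7 |
|---|---|---|---|---|
| 5 | 23% | 21% | 18% | 15% |
| 20 | 64% | 54% | 42% | 29% |
| 26 | 74% | 62% | 48% | 32% |

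The correlations are assumptions; the protocol gives none. Whatever the correlation, the expected number of false positives with 20 outcomes is 20 × 0.05 = 1.0. The paired before-and-after tests fall under the same threshold and would add further chances that the table does not count. LSD gives no protection across outcomes.

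**4. The opposite reading.** If success required every component of the hypothesis to be significant, a false claim would need at least one truly null component to cross 0.05. The probability of that is at most 5%, so there is no inflation. The protocol does not choose between the two readings.

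**The case against.** The strongest reply has four parts.

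- **The Data analysis section only says when a result is called significant.** It does not say that any single marker decides the trial. This stands. A reader might infer that whichever marker crosses 0.05 becomes the result; the text permits that but does not state it. The hypothesis is joined by *and*, so the all-must-succeed reading is open too.
- **The sections overlap rather than contradict one another.** The hypothesis includes the glucose response, which belongs to the aim, and oxidative stress, of which 8-OHdG is the protocol's marker. This also stands. Calling them three conflicting endpoints would be too strong: the fault is that none is put first and that the power belongs to a marker that does not measure glycaemia.
- **Endpoints able to test the aim are in the protocol.** HbA1c, blood glucose and OGTT glucose AUC all appear. A reader might infer that the trial has no endpoint that could confirm or refute its aim. That is wrong; what is missing is the designation.
- **A false positive somewhere need not be likely.** Several indices are built from the same glucose and insulin samples, so independence is the upper end. With 20 outcomes the figure drops below one half at a correlation of 0.5, and for a short list it is about 15% to 23%. It is also true that the 5% in the sample size paragraph belongs to one t-test and promises no trial-wide control.

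An unseen analysis plan might add a testing order or an adjustment. That would answer part of the point, but it would not repair the power basis or the undifferentiated rule that the protocol states.

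**Conclusion.** The point holds in this form: the visible protocol designates no primary endpoint, bases its power on oxidative markers although its aim is glycaemic control, and applies one P ≤ 0.05 threshold to some 20 to 26 outcomes. It can therefore yield a claim of significance on a marker unrelated to its aim.

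The size of the error depends on a rule that the protocol leaves open. If any one result sufficed, the false-positive chance would be about three to thirteen times the nominal 5% (15% to 64%) over 5 to 20 outcomes and assumed equal correlations of 0 to 0.7, counting between-arm tests only. If all parts of the hypothesis had to succeed, there would be no inflation. The misaligned power claim does not depend on any of these assumptions.

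**What to change.** - **Aims, Hypotheses and Data analysis:** name one glycaemic measure already in the protocol as the primary endpoint, for example 2-hour OGTT glucose AUC or HbA1c. Test the between-arm difference at week 12 at two-sided 0.05. The OGTT is described at both visits. The Visit 2 text does not itself name HbA1c, so that choice would need a line there.
- **Data analysis:** label all other outcomes secondary or exploratory and report them with 95% confidence intervals, not as proof of the aim. A fixed-order test of DPP-4 activity and 8-OHdG after the primary is optional. If it is used, the order is the sponsor's choice, and a failed primary ends confirmatory testing.
- **Sample size Justification:** restate power for the primary endpoint at the planned size, with its assumed difference and standard deviation, or say that the 80% applies only to 8-OHdG. The conflict between 25 and 50 per group has to be settled for this.

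**Cost.** No new visits or assays should be needed, but it is more than a change of wording. The power restatement needs an effect size and standard deviation that the document lacks, and the result may be less favourable. Isolated P ≤ 0.05 results on other markers, including DPP-4 activity, could no longer be claimed as confirmatory. The change should be made before unblinding.
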